3.3.2 Perioperative Management

Preoperative period

ERAS perioperative care principles will be emphasized. All patients will receive prophylactic antibiotics according to established guidelines. Medications will be continued perioperatively unless or at the clinicians discretion, but we will recommend withholding ACE-inhibitors and ARBs on the day of surgery. We will record preoperative use of bowel preparation, fasting times, ERAS data, medications, and biochemistry and haematology results on the CRF.

Intraoperative period

Choice of anaesthetic agents and perioperative analgesia will be left to the discretion of the anaesthetist; such data will be recorded. We will emphasize the need to avoid hypothermia (<36 °C). Epidural use will be recorded as this may

increase the risk of hypotension and need for IV fluids (64, 65), but such effects are likely to be small (66). We will record usage of all "advanced" monitoring devices (CVP, pulse contour analysis, TOE, oesophageal Doppler).

The acceptable limits of low BP, and a definition of 'hypotension', vary widely (67), though such a definition will be modified by older age, pre-existing hypertension, and cerebrovascular disease. We will use a general guideline of systolic BP <90 mmHg for more than 5 mins, but also ask the attending anaesthetist to modify their acceptable lower limit of sBP at the commencement of surgery, and, according to randomly-assigned group, treat hypotension with additional IV fluid or vasopressor therapy (see below). For example, in younger patients or those with pre-existing low BP it may be acceptable to tolerate a sBP of 85-95 mmHg, but in older patients, particularly those with pre-existing hypertension, a higher lower limit may be required. Such modification to the acceptable lower sBP will be recorded. For patients managed in a high dependency or ICU environment after surgery, hypotension will be similarly treated for the first 24 h after surgery.

Postoperative period

Patients will be followed daily and outcomes will be recorded until discharge. We will recommend that antihypertensive medications should be withheld until sBP is consistently at or above preoperative levels. Serum electrolytes, haemoglobin/haematocrit, and a 12-lead ECG will be ordered preoperatively and on day 1 after surgery. CRP will be measured on postoperative Day 3 and whenever sepsis is suspected (68, 69). Additional laboratory tests will be ordered if clinically indicated. On day 3 all patients will complete the 15-item quality of recovery score (QoR-15). On day 30 all patients will be contacted by phone to ascertain if they have experienced any outcomes, and if detected, further testing will be arranged. Documentation for such events will be sought in the hospital medical record and doctor's records. The QoR-15 will be repeated on day 30 along with WHODAS, and the WHODAS will be repeated at 3-, 6- and 12-month follow-up to ascertain survival status and new-onset disability.

3.3.3 Clinical Observations

3.3.3.1 Primary Endpoint

Disability-free survival up to 1 year: survival and freedom from disability. The latter is defined as a persistent (≥6 months) reduction in health status as measured by a 12-item version of WHODAS (70) score of at least 24 points, reflecting a disability level of at least 25% and being the threshold point between "disabled" and "not disabled" as per WHO guidelines (71). Disability will be assessed by the participant, but if unable then we will use the proxy's report. The date of onset of new disability will be recorded. Further details are provided in the Procedures Manual and the Statistical Analysis Plan.

3.3.3.2 Secondary Endpoints

Secondary endpoints include an *a priori* composite of 30-day mortality or major septic complications (sepsis, surgical site infection, anastomotic leak, and pneumonia), plus each individually, serum lactate (at 6 and 24 h), CRP (Day 3), blood transfusion, acute kidney injury, ICU and hospital stay, unplanned admission to ICU, and quality of recovery (QoR-15). We will use the following definitions:

- 1. Death: all-cause mortality at 90 days, then up to 12 months after surgery
- 2. A composite (pooled) and individual septic complications: sepsis, surgical site infection, anastomotic leak, and pneumonia
- 3. Sepsis: using Centers for Disease Control and Prevention (CDC) with National Healthcare Safety Network (NHSN) criteria:(72): two or more features of the systematic inflammatory response syndrome (SIRS) plus **evidence of a source or site of infection** (can be positive blood culture or purulence from any site):
 - i) Core temperature > 38°C or <36°C (core temperature was rectal or tympanic). If oral, inguinal or axillary temperatures were used, 0.5°C to be added to the measured value
 - ii) Heart rate > 90 beats per minute. If patient had an atrial arrhythmia, record the ventricular rate. If patients have a known medical condition or are receiving treatment that would prevent tachycardia (for example, heart block or beta blockers), they must meet two of the remaining three (a,b,c) SIRS criteria
 - a) Respiratory rate > 20 breaths per minute
 - b) $PaCO_2 < 32 \text{ mmHg } (4.3 \text{ kPa})$
 - c) mechanical ventilation for an acute process
 - iii) White cell count of >12,000 mm³ or < 4,000 mm³
- 4. Surgical site infection: using CDC criteria (http://www.cdc.gov/nhsn/PDFs/pscManual/9pscSSIcurrent.pdf):
 - i) Superficial This includes one or more of the following:

- (1) purulent drainage from the superficial incision,
- (2) organisms isolated
- (3) diagnosis by surgeon or other physician or one of the signs or symptoms of infection- (pain or tenderness, localised swelling, redness or heat, superficial incision and is deliberately opened by surgeon.) (Unless culture negative)
- ii) Deep Incisional This includes one of the following:
 - (1) Purulent discharge from deep incision but not from organ/space component of the surgical site
 - (2) A deep incision spontaneously dehisces or is deliberately opened by surgeon with one addition sign (Temperature >38°C, localised pain, tenderness)
 - (3) An abscess or other evidence of infection
 - (4) Diagnosis by surgeon or other physician
- iii) **Organ/space** Occurred within 30 days with no implant or within 1 year if an implant is in place this includes one or more of the following
 - (1) Purulent discharge
 - (2) Organisms identified
 - (3) Abscess or evidence of infection involving the organ/space on examination
 - (4) Diagnosis by surgeon or other physician
- 5. **Pneumonia:** The presence of new and/or progressive pulmonary infiltrates on chest radiograph plus two or more of the following:
 - (1) Fever ≥ 38.5°C or postoperative hypothermia <36°C
 - (2) Leukocytosis ≥ 12,000 WBC/mm³ or leukopenia < 4,000 WBC/mm³
 - (3) Purulent sputum and/or
 - (4) New onset or worsening cough or dyspnoea.
- 6. **Anastomotic leak:** A defect of the intestinal wall at the anastomotic site (including suture and staple lines of neorectal reservoirs) leading to a communication between the intra- an extra luminal compartments.
 - (1) Grade A anastomotic leakage results in no change in patients' management
 - (2) Grade B leakage requires active therapeutic intervention but is manageable without re- laparotomy
 - (3) Grade C anastomotic leakage requires re-laparotomy
- 7. Acute kidney injury: according to The Kidney Disease: Improving Global Outcomes (KDIGO) group criteria, but not urine output for Stage 2 or worse AKI defined as at least 2-fold increase in creatinine, or estimated GFR decrease >50%.(73) We also plan to report renal replacement therapy up to 90 days after surgery. Because a restrictive IV fluid regimen may artificially elevate serum creatinine due to a smaller dilutional effect from less IV fluids, we therefore calculated adjusted creatinine by first estimating the volume of distribution for creatinine as equal to total body water (assumed to be 60% of body weight, expressed in mL), and assuming that 50% of IV fluid was still accumulated as tissue oedema at the time of postoperative creatinine measurements.(74, 75) That is:

adjusted $Cr = SCr \times (1 + [0.5 \times fluid\ balance/total\ body\ water])$

- 8. Pulmonary oedema: respiratory distress or impaired oxygenation AND radiological evidence of pulmonary oedema
- 9. Duration of mechanical ventilation: additive, for all episodes up to 90 days after surgery
- 10. Inflammation: plasma C-reactive protein (CRP, using site-specific assay) concentration on Day 3
- 11. Tissue perfusion: peak serum lactate within 24 hours of surgery
- 12. **Any blood transfusion:** including red cell, fresh frozen plasma or platelet transfusion, from the commencement of surgery
- 13. Unplanned admission to ICU within 30 days of surgery
- 14. Total ICU stay: additive, including initial ICU admission and readmission times up to Day 30
- 15. **Hospital stay:** additive, from the start (date, time) of surgery until actual hospital discharge , plus readmission(s) up to Day 30
- 16. Quality of recovery: QoR-15 score(76) on days 1, 3, and 30.
- 17.

Excessive fluid resuscitation can cause haemodilution (64) and dilutional coagulopathy, and this may increase the need for red cell and other blood transfusion (32). Blood transfusion is, of itself, associated with increased rates of sepsis and other postoperative complications (3, 24). All patients will have the same red cell transfusion trigger of 70 g/L, but this can be modified after assessment of cardiovascular risk (77, 78) or concern for active bleeding. Normal Saline, containing 154 mmol of sodium and 154 mmol of chloride per litre, is non-physiological and can lead to hyperchloraemic acidosis (33) and perhaps poorer outcome (79, 80). We will use a balanced salt solution as the routine fluid therapy in this study. The questionable value of urine output as a measure of kidney or other tissue perfusion will be emphasized (81).

Our study Group fluid regimens are aimed at distinct volume differences and according to recent recommendations (4, 72). The group-assigned fluid regimens will continue for at least 24 hours after surgery, or until cessation of IV fluid therapy (whichever occurs first). If the patient's clinical condition warrants modification to the type or rate of fluid administration, then such modifications can be made immediately. This does NOT imply that the patient is removed from the trial because we will analyze according to the intention-to-treat principle, but we will collect such data for secondary per-protocol and sensitivity analyses.

Management of Oliguria

It is a normal response of the body to attempt to conserve fluid in times of physiological stress. Oliguria (low urine output) is part of this homeostatic mechanism; there is no evidence it is harmful in the short term (first 24-48 h after surgery is common and not abnormal) (81). Nor is there any evidence that diuretics protect against AKI (82). We will however provide guidance to ward medical and nursing staff (see Procedures Manual).

4. Experimental control

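### The sepsis definition's exception for patients who cannot mount tachycardia points only to respiratory signs and conflicts with the general two-feature SIRS rule

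*Protocol*

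**What the plan says.** The sepsis definition (Protocol 3.3.3.2, definition 3) opens with a general rule: "two or more features of the systematic inflammatory response syndrome (SIRS) plus" evidence of a source or site of infection. Three features carry roman numerals: i) temperature, ii) heart rate, iii) white cell count.

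The heart-rate item contains an exception for patients with a known condition, or on treatment, that would prevent tachycardia; heart block and beta blockers are the examples given. For them, "they must meet two of the remaining three (a,b,c) SIRS criteria".

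Three lettered items follow, before item iii: a) "Respiratory rate > 20 breaths per minute"; b) PaCO2 below 32 mmHg; c) "mechanical ventilation for an acute process". They have no heading or roman numeral of their own.

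Sepsis is one component of the 30-day composite of mortality or major septic complications and is also reported individually. The composite is a secondary hypothesis in Protocol 1.1. The SAP (Secondary endpoints, item 2) gives no sepsis definition and refers back to the Protocol. Under Subgroup analyses it also examines the composite across the planned subgroups.

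**The concern.** The exception and the general rule give different answers for the same patient. Someone on a beta blocker with proven infection, fever and an abnormal white count has two SIRS features under the general rule, yet has none of the two lettered items that the exception demands. A patient with a fast respiratory rate and a low PaCO2, but normal temperature and white count, meets the exception on respiratory signs alone.

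At stake is how sepsis is counted in the excepted patients, and through it one component of the secondary composite. A rule that staff must interpret for themselves is a particular weakness here, because Protocol 4.3 accepts that those conducting in-hospital daily reviews cannot be properly blinded.

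**Working it through.** The plan states no figure on this point, so the check is one of logic.

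**Step 1: what the letters denote.** The letters appear inside the exception sentence and match the three printed respiratory items. Nothing else in the definition is lettered a, b or c.

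**Step 2: what the three remaining criteria could be.** Three counts are possible once heart rate is set aside:
- The roman-numbered list leaves two (temperature, white count).
- Counting each respiratory item as its own feature leaves five (temperature, white count, a, b, c).
- Treating the respiratory items as one criterion leaves three (temperature, respiratory, white count).

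Only the last gives three remaining SIRS criteria in the ordinary sense. The likely intent is therefore four criteria, with heart rate set aside. The letters point elsewhere.

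**Step 3: example patients covered by the exception, all with evidence of infection.**

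| Abnormal signs | As lettered: two of a, b, c | Two of temperature, respiratory, white count |
|---|---|---|
| Temperature and white count | 0: no | 2: yes |
| Temperature and respiratory rate | 1: no | 2: yes |
| White count and respiratory rate | 1: no | 2: yes |
| Respiratory rate and PaCO2 | 2: yes | 1: no |
| Temperature, respiratory rate and PaCO2 | 2: yes | 2: yes |

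**Step 4: all patterns.** Five signs, each present or absent, give 2^5 = 32 patterns.
- As lettered: 4 of the 8 respiratory patterns have at least two signs. Times 4 temperature and white-count patterns: 4 × 4 = 16 qualify.
- Alternative reading: with both temperature and white count abnormal, all 8 respiratory patterns qualify. With exactly one of them abnormal, 2 × 7 = 14 qualify. Total 8 + 14 = 22.
- Both readings: 4 × 3 = 12.
- Alternative only: 22 − 12 = 10. Of these, 4 have temperature and white count abnormal with at most one respiratory sign, and 6 have one of the two abnormal with exactly one respiratory sign.
- As lettered only: 16 − 12 = 4, all with at least two respiratory signs and normal temperature and white count.

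The readings disagree on 10 + 4 = 14 of 32 patterns, in both directions. The patterns are not equally likely in patients, so this says nothing about frequency.

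**Step 5: is it corrected elsewhere?** The SAP defers to the Protocol. Protocol 9.5 lets the adjudication committee resolve uncertainty about outcomes but gives no other sepsis rule.

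**The case against.** The best defence is that this is a slip of labelling that any clinician would read through. The governing rule is two or more SIRS features, the phrase about the remaining three shows the intent, and staff probably applied it that way. The Procedures Manual and CRF, which are not available here, may state it correctly, and disputes go to blinded assessors (Protocol 5). Much of this stands. The realistic harm is ambiguous or inconsistent coding, not certain exclusion. It does not remove the contradiction, because the Protocol text is the only definition that the SAP relies on.

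A second defence is that list nesting may have been lost when the PDF was read. That carries little weight: the letters are in the sentence itself, so indentation does not explain the mismatch.

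A third is that the composite is cushioned. Surgical site infection, anastomotic leak and pneumonia are separate components. Purulent wound drainage can itself count as surgical site infection, and new infiltrates with sufficient fever and leukocytosis count as pneumonia. This stands: some patients missed as sepsis would still enter the composite.

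A reader might also infer more than the documents support:
- **A percentage of sepsis events lost.** This needs the share of patients under the exception and the share of their cases lacking two respiratory signs. Neither is given.
- **Losses concentrated where sepsis is most likely.** Coronary disease and heart failure are only two of several alternative entry criteria (Protocol 3.2.3), and no sepsis risk by subgroup is reported.
- **A loss of power.** The error runs both ways, and its net effect on the composite is unknown.
- **Bias between arms.** Protocol 2.1 cites less pulmonary oedema with fluid restriction, so respiratory signs might differ by arm. But entry to the exception depends on a condition or treatment that prevents tachycardia, not on fluid group, and nothing shows differential misclassification.

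**Conclusion.** The point holds as an internal inconsistency in a secondary-endpoint definition. Taken literally, the exception leaves out temperature and white count, rejects a combination that the general rule accepts, and admits patients on respiratory signs alone.

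The first two parts follow directly from the text. The claim that respiratory signs alone are too lenient assumes that the respiratory items form a single SIRS criterion, which the count of three supports but the definition does not state. If each were a separate feature, two respiratory signs would also satisfy the general rule, and only the rejection of qualifying patients would remain.

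The effect is confined to sepsis as an individual outcome and to the 30-day composite, including its subgroup analyses. The primary endpoint is unaffected. The number of events misclassified cannot be estimated from the documents, and whether assessors followed the letters or the general rule is unknown.

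**What to change.** - List four SIRS criteria at one level: temperature; heart rate; respiratory (rate, PaCO2 or ventilation); white cell count. This also settles, for every patient, that the respiratory items count once.
- Reword the exception to require two of the remaining three: temperature, respiratory, white cell count.
- Use the same wording in the CRF logic and the adjudication instructions, and check the Procedures Manual against it.
- Where data are already collected, state which rule was applied and re-derive sepsis under the reworded rule, blinded to allocation, wherever the component signs were recorded. This is likely to matter, since Protocol 6 reports 2,578 patients enrolled at the June 2016 review and the SAP is dated August 2017.

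The wording change costs almost nothing and adds no new measurement to the definition. Re-derivation costs some data-management and adjudication time, and is possible only where the individual signs, not just the sepsis verdict, were captured.

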4.1 Group assignment

This will be a large, randomized, parallel-group, controlled trial. After stratification by centre and planned ICU/HDU admission (or not), patients will be randomly assigned from a computer-generated list (1:1) to either a Restrictive or Liberal fluid Group.

A 24-hr interactive voice recognition system (IVRS) will be available. An alternative web-based randomisation service will also be available during the conduct of the trial.

This is an intention to treat trial. Any participant who is randomised will be followed for the duration of the trial (unless they withdraw consent) even if they are withdrawn from the active phase of the trial. Patients who do not complete the active phase of the study will not be replaced.

[figure not shown]
Liberal Protocol

The Liberal protocol group reflects common contemporary practices in Australia(29, 82), and is consistent with previous international trials (20, 24, 83) – see Appendix. At the commencement of surgery a bolus of Hartmann's balanced salt crystalloid 10 ml/kg followed by 8 ml/kg/h will be administered until the end of surgery – the latter can be further down-titrated after 4 hours if clinically indicated. Important: for the purposes of calculations of bolus and maintenance fluids in patients exceeding 100 kg, the maximal body weight will be set at 100 kg. A maintenance infusion will then continue at 1.5 ml/kg/h, for at least 24 hours, but this can be reduced postoperatively if there is evidence of fluid overload and no hypotension, and increased if there is evidence of hypovolaemia or hypotension. Alternative fluid types (crystalloid, dextrose, colloid) and electrolyte supplements will be allowed postoperatively in order to account for local preferences and patient biochemistry, for which we will collect data. For a 75-kg adult, the intraoperative volume (for a 4 h operation) will be 3150 ml (+colloid/blood replacement for blood loss), and then around 2700 ml per day. That is, the first (intraoperative + postoperative) 24-h fluid administration will be about 5400 ml (P.T.O).

Restrictive Protocol

The Restrictive protocol group is designed to provide less than 2.0 L water and 120 mmol sodium per day. Induction of anaesthesia will be accompanied by an IV fluid bolus limited to ≤5 ml/kg; no other IV fluids will be used at the commencement of surgery (unless indicated by goal-directed device [see below]). Hartmann's balanced salt crystalloid 5 ml/kg/h will be administered until the end of surgery, and bolus colloid/blood used intraoperatively to replace blood loss (ml for ml); then an infusion at 0.8 ml/kg/h until expedited cessation of IV fluid therapy within 24 hours. The rate of postoperative fluid replacement can be reduced if there is evidence of fluid overload and no hypotension, and can

be increased if there is hypotension AND evidence of hypovolaemia. For a 75-kg patient and 4 h operation, intraoperative fluid volume will be 1875 ml (+colloid/blood replacement for blood loss). The first 24-h fluid administration will be around half that of the liberal group (P.T.O).

Hypotension will be initially treated with fluid boluses in the liberal protocol group, and with a vasoconstrictor in the restrictive protocol group. The latter will consist of metaraminol or phenylephrine bolus/infusion and/or noradrenaline infusion during surgery, and a noradrenaline infusion postoperatively if in a HDU or ICU environment. The lower limit of acceptable sBP in the restrictive group can be further reduced by the attending anaesthetist or intensivist in order to limit fluid replacement or potentially unnecessary inotropic support (as per above). We have laminated instructional flowcharts for the anaesthetists and postoperative (ward or ICU/HDU) medical and nursing staff caring for the study patients (see Appendix). Research staff will be present at or soon after all handover steps, and be contactable at all hours.

4.2 Goal-directed Therapy

For anaesthetists employing advanced monitoring (eg. CVP or goal-directed device), we allow additional colloid fluid supplementation to augment a haemodynamic target. It is likely to lead to additional colloid administration during and after surgery (3, 4, 45). Some hospitals use pulse contour analysis to direct perioperative or ICU fluid therapy in surgical patients, and some use oesophageal Doppler. Most rely upon conventional monitoring (HR, BP, urine output). We plan to test the effectiveness of each approach according to their local availability and use. The statistical analysis will focus

on a test for interaction, to determine whether the effects of a fluid regimen work differently in those with and without any advanced monitoring. We anticipate that more than half will use (only) clinical measures.

For each of the goal-directed techniques, pulse/stroke volume variation or FTc will be measured before commencement of surgery and repeated at regular (say, 10-30 min) intervals intraoperatively. For those in the liberal protocol group, goal-directed therapy can continue postoperatively at 4 hourly intervals, for up to 24 hours after surgery. If there is evidence of fluid responsiveness (eg. systolic pressure/volume variation of ≥13% (77)) at any of these times then IV colloid or crystalloid 3-5 ml/kg can be given. Such data will be collected on the CRF.

Colloid* (recommended) or crystalloid (3 ml/kg)	Liberal	Restrictive
Colloid/blood (using a transfusion threshold) bolus if acute bleeding	Yes	Yes
If normotensive but monitoring suggests hypovolaemia (eg. CVP<5 or oliguria)	Yes	No
If normotensive but goal-directed device suggests hypovolaemia (eg. FTc <0.33, ΔSV ≥10%, or SVV≥13%)	Yes	Consider
If hypotensive (1) and hypovolaemia	Colloid*	Colloid* (but limit) + vasoconstrictor
(2) but not hypovolaemic	Colloid* ± vasoactive	vasoactive therapy

^{*} starch-based colloids are not recommended (30, 34)

